## 5.6 Secondary/Exploratory Endpoints – IGA 0/1 and EASI 50/75/90

Secondary endpoints, EASI 50 and EASI 90 at week 16 in Part A, and Exploratory endpoints, IGA 0/1 at week 24, week 36 and week 52 in Part A and B, and IGA 0/1 at week 16 in Part B, will be defined in the same way as primary endpoints in [Section 5.5](#). For example, the time point of interest is week 24, week 36 and week 52 instead of week 16, the use of TCS/TCI will be considered from day 29, to week 24, week 36 and week 52 respectively.

Time-to-event analysis of EASI 50/75/90 will be handled as described in [Section 9.5.2](#) and [Section 9.5.3](#).

In addition, IGA 0/1 and EASI 75 at time points other than week 16, week 24, week 36 and week 52 in both Part A and B will be defined in the same way as primary endpoints in [Section 5.5](#) at corresponding time points. For example, when the time point of interest is week 4, week 6, week 8, week 10, and week 12 instead of week 16, the use of TCS/TCI will be considered from day 29, to those time points respectively.

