Part A is a dose-ranging, randomized, placebo-controlled, double-blind study designed to evaluate the safety and efficacy of tezepelumab as monotherapy in subjects with moderate-to-severe AD. Following the screening period, eligible subjects will be randomized 1:1:1:1 to receive 420 mg SC Q2W, 280 mg SC Q2W, 210 mg SC Q4W, or placebo. All subjects will receive a 420 mg SC dose (investigational product or placebo) as the first dose. Subjects will then receive the appropriate dose of investigational product at the week 2 visit, depending on which treatment group they are randomized to. Depending on if they are randomized to Q2W or Q4W dosing, the dose at week 2 could be placebo or tezepelumab. Non-responders are defined as those subjects who have not achieved at least a 50% improvement in EASI at week 16 compared to baseline (day 1). Subjects who are determined to be non-responders in Part A will receive tezepelumab 420 mg SC Q2W for the remainder of the study, beginning with the

week 18 dose. The randomized treatment assignments for the non-responders will remain blinded until the end of study.

Part B is a randomized, placebo-controlled, double-blind study designed to evaluate the safety and efficacy of tezepelumab when administered with moderate class TCS in adults with moderate-to-severe AD. Enrollment of subjects in Part B of the study will only commence if there is a result of “not futile” for the first interim analysis in Part A and Part A has completed enrollment of 240 patients. Following the screening period, eligible subjects will be randomized 2:1 to receive 420 mg SC Q2W or placebo; both groups in Part B will be allowed to use TCS after the day 1 visit. Non-responders in Part B will not be switched to 420 mg SC Q2W at week 18 and will remain on their initial dose for the duration of the study.

The overall study design is described by a study schema in [Section 2.1](#). The endpoints are defined in [Section 4.1](#).

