If the lesions return, subjects are to resume treatment with medium potency TCS, and are to use the step-down approach to low potency TCS described above. For lesions that persist or worsen with once daily application of medium potency TCS, subjects may be treated (further rescued) with high or super-high potency TCS, unless higher potency TCS is considered unsafe.

Part B

Additionally, in Part B of the study, subjects are allowed to apply TCS following completion of all day 1 activities. Subjects should bring their containers of TCS to the site at every visit to have the container weighed and the amount of TCS used since the previous visit recorded.

Subjects who use TCS are to apply medium potency TCS once daily to areas with active lesions. Low potency TCS should be used once daily on areas of thin skin (eg, face, neck, intertriginous, genital areas, areas of skin atrophy) or for areas where continued treatment with medium potency TCS is considered unsafe. Triamcinolone acetonide 0.1% cream or fluocinolone acetonide 0.025% ointment are recommended as medium potency TCS therapy; hydrocortisone 1% cream is recommended as low potency TCS therapy. After lesions are under control (clear or almost clear), subjects are to switch from medium potency to low potency TCS and treat once daily for 7 days, then cease TCS therapy.

If the lesions return, subjects are to resume treatment with medium potency TCS, and are to use the step-down approach to low potency TCS described above. For lesions that persist or worsen with once daily application of medium potency TCS, subjects may be treated (rescued) with high or super-high potency TCS, unless higher potency TCS is considered unsafe.

In Part B, after all week 2 activities are completed, if needed to control intolerable symptoms, subjects may receive rescue treatment with any approved AD therapy (see [Section 7.1.7](#) for excluded treatments). If rescue with TCS is necessary, mometasone 0.1% ointment is recommended as a high potency therapy; betamethasone dipropionate 0.05% optimized ointment or clobetasol propionate 0.05% cream are recommended as super-high potency therapy.

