## 2. Objectives, Endpoints and Hypotheses

### 2.1 Objectives and Endpoints

Objectives	Endpoints
Primary – Part A	

To evaluate the effect of tezepelumab compared with placebo, assessed using the Investigator's Global Assessment (IGA) and Eczema Area and Severity Index (EASI)

	

IGA score of 0 (clear) or 1 (almost clear) (IGA 0/1) at week 16

75% reduction in EASI (EASI 75) at week 16

The first primary estimand consists of:

- Target population – patients with moderate-to-severe atopic dermatitis (**AD**).
- Endpoint – IGA 0/1 at week 16.
- Intercurrent event – there are 2 intercurrent events, discontinuation of IP before week 16 and **concurrent use** of rescue medication **with TCS/TCI** between day **29** and week 16. Treatment effects will be estimated for subjects regardless of whether patients complete 16 weeks of **study treatment**. The use of rescue medication is captured through the endpoint definition in **Section 5.5, and use of TCS/TCI will be classed as a non-response**.
- Summary measure – odds ratio comparing the odds of achieving endpoint on tezepelumab 420 mg Q2W compared to the odds of achieving endpoint on placebo.

In summary, the first primary estimand is the odds ratio between tezepelumab 420 mg Q2W and placebo in achieving IGA 0/1 at week 16, in the absence of rescue medication with **TCS/TCI regardless of whether patients complete 16 weeks of study treatment**, in patients with moderate-to-severe AD.

The second primary estimand is the odds ratio between tezepelumab 280 mg Q2W and placebo in achieving IGA 0/1 at week 16, in the absence of rescue medication with **TCS/TCI regardless of whether patients complete 16 weeks of study treatment**, in patients with moderate-to-severe AD.

The third primary estimand is the odds ratio between tezepelumab 420 mg Q2W and placebo in achieving EASI 75 at week 16, in the absence of rescue medication with **TCS/TCI regardless of whether patients complete 16 weeks of study treatment**, in patients with moderate-to-severe AD.

The fourth primary estimand is the odds ratio between tezepelumab 280 mg Q2W and placebo in achieving EASI 75 at week 16, in the absence of rescue medication with **TCS/TCI regardless of whether patients complete 16 weeks of study treatment**, in patients with moderate-to-severe AD.

Secondary – Part A	

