### Eczema Area and Severity Index (EASI)

The EASI is designed by modifying the Psoriasis Area and Severity Index, which has been widely used in clinical trials and has been established as a well-accepted and standardized instrument for assessing therapeutic response in patients with psoriasis ([Schmitt et al, 2007](#)). The EASI evaluates 4 natural anatomical regions for severity and extent of key disease signs and focuses on key acute and chronic signs of inflammation (ie, erythema, induration/papulation, excoriation, and lichenification). The maximum score is 72, with higher values indicating more severe disease.

For subjects who take rescue medication of TCS/TCI from day 29, their EASI score will be ignored on and after the date of rescue medication.

Body Region	Severity	Area	Score
Head/Neck (H)	The average degree of severity of each sign (erythema [E], induration/papulation [I], excoriation [EX] and lichenification [L], is defined on a 4-point ordinal scale:  0 = none 1 = mild 2 = moderate 3 = severe	The area is defined on a 7-point ordinal scale:  0 = no eruption 1 = <10% 2 = 10% - 29% 3 = 30% - 49% 4 = 50% - 69% 5 = 70% - 89% 6 = 90% - 100%	$(E+I+EX+L) * Area * 0.1$
Upper Limbs (UL)			$(E+I+EX+L) * Area * 0.2$
Trunk (T)			$(E+I+EX+L) * Area * 0.3$
Lower Limbs (LL)			$(E+I+EX+L) * Area * 0.4$
EASI Score			Sum of scores of H, UL, T, and LL

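### SAP 5.6 carries the Part A TCS/TCI non-response rule into Part B unadapted, without saying whether background TCS counts or from which day Part B rescue counts

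*SAP*

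**What the plan says.** **The source rule (SAP 5.5).** For the Part A primary endpoints, response at week 16 requires the clinical criterion and no rescue TCS/TCI from day 29 to week 16. A missing assessment without known rescue is left missing; every other case is 0. The Part A estimand text in SAP 2.1 adds that "use of TCS/TCI will be classed as a non-response".

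**The extension (SAP 5.6).** The first sentence covers EASI 50 and 90 at week 16 in Part A, IGA 0/1 at weeks 24, 36 and 52 in both parts, "and IGA 0/1 at week 16 in Part B, will be defined in the same way as primary endpoints". The example that follows says "the use of TCS/TCI will be considered from day 29, to week 24, week 36 and week 52 respectively". A later paragraph takes IGA 0/1 and EASI 75 at the remaining visits and says that these "in both Part A and B will be defined in the same way as primary endpoints". Its example again refers to use of TCS/TCI from day 29. The word rescue appears in neither example.

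**TCS in Part B (protocol).** Section 5.1 states that "both groups in Part B will be allowed to use TCS after the day 1 visit". Section 7.1.5 sets out the Part B regimen: "Subjects who use TCS are to apply medium potency TCS once daily to areas with active lesions", with low potency for thin skin and as a step-down. Sections 7.1.5 and 7.1.7 attach the rescue label in Part B to high or super-high potency TCS, to TCI, and to other approved AD therapy after week 2.

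**Related rules.** SAP 5.4 says: "For subjects who take rescue medication of TCS/TCI from day 29, their EASI score will be ignored on and after the date of rescue medication". Similar sentences cover the other scores. The Part B paragraph of SAP 9.5.3 censors time to EASI response at rescue from day 29. Neither place says what rescue means in Part B.

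**The concern.** In Part A, TCS use and rescue use are nearly the same event, so the shorthand does no harm there. In Part B they differ, because low and medium potency TCS is part of what both arms may use. Part B is there to estimate tezepelumab plus TCS against placebo plus TCS. A rule that scores any TCS use after day 28 as failure would instead estimate response without TCS. It would also tie the result to how much TCS each arm uses, and TCS use plausibly depends on disease activity and therefore on treatment.

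The SAP states estimands only for Part A, so nothing else in it settles which reading was meant. Two programmers working from the same text could produce different Part B response rates.

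**Working it through.** **1. Which Part B endpoints the rule reaches**

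| Part B endpoint | Treatment in SAP 5.6 |
|---|---|
| IGA 0/1, weeks 16, 24, 36, 52 | Named; defined as in 5.5 |
| IGA 0/1 and EASI 75, other visits | Named; defined as in 5.5 |
| EASI 75, weeks 16, 24, 36, 52 | Not named |
| EASI 50 and 90 | Covered by the section title only |

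**2. One subject under the two readings.** Take a Part B subject who applies medium potency TCS as protocol 7.1.5 describes, at some time between day 29 and week 16, receives nothing the protocol calls rescue, and is IGA 0 at week 16.

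- Literal 5.6 reading (any TCS use counts): the response condition fails, the assessment is not missing, so the remaining-cases rule gives 0.
- Rescue-only reading (5.5 wording with the protocol's Part B labels): no rescue occurred, so the result is 1.

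**3. The start day.** SAP Appendix A sets the target day as week × 7 + 1, so week 2 is day 15 and week 4 is day 29.

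- Part A bars rescue in the first 4 weeks, which matches day 29.
- Part B allows rescue once week 2 activities are complete, from about day 15.
- Part B rescue between about day 15 and day 28 (28 − 15 + 1 = 14 days) is therefore not counted on either reading. At the week 4 visit, which 5.6 names, the period considered runs from day 29 to a target day of 29, so essentially no earlier rescue enters.

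**4. The plan's own Part B figure.** SAP 3.2 gives 40 versus 20 subjects, example differences of 30 points (IGA 0/1) and 35 points (EASI 75), and a 95% CI half-width of about 20%. I assume that the Part A planning rates underlie the example (40% vs 10%; 50% vs 15%).

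Half-width = 1.96 × √[p₁(1−p₁)/40 + p₂(1−p₂)/20]

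- IGA 0/1: 1.96 × √(0.24/40 + 0.09/20) = 1.96 × √0.0105 = 20.1 points
- EASI 75: 1.96 × √(0.25/40 + 0.1275/20) = 1.96 × √0.012625 = 22.0 points

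The figure reproduces for IGA and is loosely rounded for EASI.

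**5. Size under the literal reading.** The documents give no rate of TCS use after day 28, so the use rate u is an assumption, taken as unrelated to response. Observed rate = true rate × (1 − u). With equal use in both arms, the difference shrinks by the same factor:

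| u, both arms | IGA 0/1 difference | EASI 75 difference, if the same rule applies |
|---|---|---|
| 0% | 30.0 | 35.0 |
| 25% | 22.5 | 26.3 |
| 50% | 15.0 | 17.5 |
| 75% | 7.5 | 8.8 |
| 90% | 3.0 | 3.5 |
| 100% | 0 | 0 |

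Odds ratios for IGA 0/1:

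- No rule: (0.40/0.60)/(0.10/0.90) = 6.0.
- 70% use in both arms: 12% vs 3%, (0.12/0.88)/(0.03/0.97) = 4.4.
- 60% use on tezepelumab, 80% on placebo: 16% vs 2%, (0.16/0.84)/(0.02/0.98) = 9.3.
- 100% use in both arms: 0/40 vs 0/20, and no odds ratio can be estimated.

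If true response were 30% in both arms, with 50% use on tezepelumab and 80% on placebo, the observed rates would be 15% and 6%: a 9-point difference with no true difference. Under the rescue-only reading, background TCS changes none of these figures.

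**The case against.** The strongest reply is that SAP 5.6 contains no derivation of its own. It points to 5.5, whose conditions are all about rescue medication, and the phrase on use of TCS/TCI only illustrates how the time window moves. SAP 5.4 and the Part B censoring text also say rescue, and the protocol separates background from rescue TCS in Part B. On that reading a background user with clear skin is a responder.

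Much of this stands. A reader might infer from 5.6 that Part B background users will certainly be scored as non-responders. The documents do not establish that; it is one of two open readings. A reader might also infer that SAP 5.4 discards their SCORAD, pruritus and other scores, but those sentences are limited to rescue. Nor does the rule expressly govern every Part B responder endpoint, as the first table shows. The estimand sentence in SAP 2.1 belongs to Part A and cannot decide the matter for Part B.

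What the reply does not remove is the gap. The SAP never says which TCS is rescue in Part B, and 5.6 drops the limiting word in both of its examples. The rescue-only reading still carries a start day that fits only Part A. It also covers only TCS/TCI, although the protocol permits Part B rescue with any approved AD therapy. Other Part B text appears to have been taken over from Part A: the time-to-response paragraph in 9.5.3 refers to switching, and Part B has no switch.

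**Conclusion.** The point holds as an undefined Part B rule with two materially different readings, a start day that does not match Part B, and missing derivations for some EASI endpoints. If the literal reading were programmed, the IGA 0/1 estimate would not answer the adjunct-therapy question. The planned 30-point difference would fall to 15 points at 50% use and 3 points at 90% use, and unequal use could push the odds ratio above or below its true value. These figures are illustrations. They rest on assumed use rates, on use being unrelated to response, and on Part A planning rates. The documents show neither the actual size nor the direction of any bias. If the rescue-only reading were programmed, only the start day, the scope of rescue and the EASI gap would remain.

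A reader might infer that the trial's main result is at risk. It is not: Part B is an estimation study with no formal test, and Part A's primary analysis, power and type I error are unaffected. Estimation is, however, Part B's only efficacy purpose, so the rule should be settled before the Part B week 16 analysis.

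**What to change.** Give Part B its own derivation in SAP 5.6, and use the same definition in the score-handling rules of 5.4 and the Part B paragraph of 9.5.3. It should state that:

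- background TCS as described for Part B in protocol 7.1.5 neither makes a subject a non-responder nor removes or censors data;
- only treatment that the protocol labels as rescue in Part B counts, from the day on which the protocol allows it in Part B;
- Part B EASI 75 at weeks 16, 24, 36 and 52, and Part B EASI 50 and 90, follow the same rule.

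Keep the present TCS/TCI rule for Part A only, and delete the reference to switching from the Part B paragraph of 9.5.3.

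The cost is SAP wording and programming. Part B TCS use is already tracked by visit in the Schedule of Activities, containers are weighed (protocol 7.1.5), and therapy names with start and stop dates are collected (protocol 7.8.2). The documents do not show whether the case report form codes potency; if it does not, potency can be mapped from the recorded product name.

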AD = atopic dermatitis; DLQI = Dermatology Life Quality Index; EASI = Eczema Area and Severity Index; ECG = electrocardiogram; Echo = echocardiogram; eCRF = electronic case report form; EOT = end of treatment; EQ-5D-3L = EuroQOL quality of life 5-dimensions 3-level version; HIV = human immunodeficiency virus; Ig = immunoglobulin; IGA = Investigator's Global Assessment; NRS = numeric rating scale; PD = pharmacodynamics; PGI-S = Patient's Global Impression of Severity; PK = pharmacokinetics; PPD = purified protein derivate; POEM = Patient Oriented Eczema Measure; S. aureus = *Staphylococcus aureus*; SCORAD = Scoring Atopic Dermatitis; TCS = topical corticosteroids; Q4W = every 4 weeks; Wk = Week

^a The screening visit can occur up to 28 days + 7 days before the first dose of investigational product on day 1.

^b The window for visits is ± 3 days.

^c ECG must be collected prior to any blood draws.

^d Vital signs will be taken pre-dose prior to administration of investigational product. Subjects will be observed for 2 hours post-treatment at the day 1 and week 2 visits.

For all other visits where investigational product is administered, subjects will be observed for a **period of time at the discretion of the Investigator**.

^e Pregnancy testing applies to females of childbearing potential only, as defined in the protocol. The pregnancy test at screening must be a serum pregnancy test. All other scheduled pregnancy tests will be urine tests. Additional on-treatment pregnancy testing may be performed at the investigator's discretion if there is suspicion that a female subject is pregnant or per local laws and regulations. If a urine pregnancy test is positive, a confirmatory serum pregnancy test will be performed by the study center and entered into the eCRF.

^f This includes total serum IgE, IgA, IgG, and IgM. All immunoglobulin results will be redacted from laboratory reports.

^g The eDiary includes Pruritus NRS.

^k PK samples at day 1 and weeks 2, 4, 12, 16, 24, 32, 40, 48, and 50 should be collected before dosing with investigational product (trough).

^l This is an optional assessment and requires an additional consent form. The sample for DNA analysis will be obtained at the day 1 visit using the cell pellet from a plasma sample taken on the same day.

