3.1 Study Rationale

Tezepelumab is being developed for the treatment of atopic dermatitis (AD). Thymic stromal lymphopoietin (TSLP) is an epithelial cytokine shown to be elevated in skin lesions of patients with AD. A previous phase 2a study (ALLEVIAD) demonstrated improvements in Investigator's Global Assessment (IGA) and Eczema Area and Severity Index (EASI) scoring, but did not meet statistical significance in the primary endpoint. A phase 1b study demonstrated improvement in IGA and EASI as secondary endpoints.

In the ALLEVIAD study, not achieving statistical significance for the primary endpoint may have been due to the patient population selected, key study design elements surrounding topical corticosteroid (TCS) use, and length of treatment.

In the ALLEVIAD study, a small number of enrolled patients (20%) had severe disease and most had moderate AD (as determined by IGA score). The current study requires a minimum of a 2-year history of AD and a higher EASI minimum score of 16, which may lead to a greater treatment effect and is consistent with other studies of biologic therapies for AD ([Simpson et al, 2016](#)).

Patients were not required to be refractory to TCS at baseline (a requirement for the current study), and received TCS during the run-in and treatment periods. The study design did not exclude responders after the 2-week run-in period, which may have contributed to the large placebo response observed.

In the ALLEVIAD study, placebo-treated patients applied greater TCS amounts during treatment versus tezepelumab-treated patients. In addition, all patients liberally applied high-strength TCS during the 2-week run-in period. These 2 factors potentially decreased the differential effect due to tezepelumab treatment. In the monotherapy design for Part A of the current study, subjects will wash out from TCS and are required to abstain from TCS use for 16 weeks. This design has been used for other therapies and will allow for an evaluation of efficacy with less potential confounding ([Simpson et al, 2016](#)).

Second, the 12-week treatment period in ALLEVIAD may not have been of sufficient duration to demonstrate efficacy in the AD population. Dosing was through week 10, thus, steady-state exposures to tezepelumab were likely not attained. In the current study, the longer treatment duration evaluation of the primary endpoint at week 16 will ensure that tezepelumab reaches steady-state concentrations.

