7.1.5 Other Treatment Procedures

During the 28-day screening period, subjects must discontinue from all AD therapies, except for approved moisturizers (see [Section 7.1.7](#)), for at least the 7 consecutive days immediately prior to day 1. During the study, approved moisturizers are allowed to be applied, with the exception of 8 hours prior to any scheduled visit.

Medications and procedures permitted at any time during the study for subjects enrolled in Part A and Part B include:

- Basic skin care (cleansing and bathing), emollients, bleach baths, topical anesthetics, and antihistamines (all for any duration)
- Medications used to treat chronic diseases such as diabetes, hypertension, and asthma

Part A

In Part A of the study, if needed to control intolerable AD symptoms, rescue treatment for AD may be provided at the discretion of the investigator. Rescue is not allowed in the first 4 weeks of Part A. Topical calcineurin inhibitors may be used for rescue, but are to be reserved for problem areas only (eg, face, neck, intertriginous and genital areas). Investigators are to attempt to limit the first step of rescue therapy to topical medications, and escalate to systemic medications only for subjects who do not respond adequately following at least 7 days of topical treatment. If a subject receives rescue treatment with systemic corticosteroids or nonsteroidal systemic immunosuppressive drugs

(eg, cyclosporine, mycophenolate-mofetil, azathioprine), study treatment is to be immediately discontinued.

All subjects are to complete the schedule of study visits and assessments whether or not they complete study treatment or receive rescue treatment for AD.

Part A Rescue Guidance

Subjects who use TCS are to apply medium potency TCS once daily to areas with active lesions. Low potency TCS should be used once daily on areas of thin skin (eg, face, neck, intertriginous, genital areas, areas of skin atrophy) or for areas where continued treatment with medium potency TCS is considered unsafe.

Triamcinolone acetonide 0.1% cream or fluocinolone acetonide 0.025% ointment are recommended as medium potency TCS therapy; hydrocortisone 1% cream is recommended as low potency TCS therapy. After lesions are under control (clear or almost clear), subjects are to switch from medium potency to low potency TCS and treat once daily for 7 days, then cease TCS therapy.

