#### 9.5.2 Analyses of Secondary Efficacy Endpoint(s)

The secondary estimands will be analyzed using **FAS – Part A**. Secondary endpoints are defined in [Section 5.6](#).

For the binary endpoint, EASI 50/90 at week 16, the treatment effect will be **analyzed** using a logistic regression model adjusting for baseline EASI. From this model, odds ratio and 95% CIs will be reported comparing each tezepelumab dose group to placebo.

The time to achieving EASI 50/75/90 response prior to switching to tezepelumab 420 mg Q2W will be summarized by Kaplan-Meier (KM) curves, the number of subjects achieving EASI 50/75/90 and the number of subjects censored will be provided at available time points. Subjects who do not achieve EASI 50/75/90 will be censored at the date when formal assessments of non-responder (as defined in protocol, that is, not achieve at least 50% improvement in EASI at week 16

compared to baseline) are recorded or end of study date, whichever is the earliest. Subjects who receive rescue medication from day 29 will be censored at the point when subjects receive rescue medication.

The treatment effect for change from baseline in SCORAD and Pruritus NRS each at week 16 will be analyzed using a **Mixed Model for Repeated Measures (MMRM)**. The model for change from baseline in SCORAD at week 16 will include visit and baseline SCORAD as covariates and an interaction term between arm and visit. The model for change from baseline in Pruritus NRS at week 16 will include visit and baseline Pruritus NRS as covariates and an interaction term between arm and visit. **AR(1) variance-covariance structure will be used.** Least square means and corresponding 95% CI will be calculated for each treatment group and for the difference between treatment groups.

Serum concentration will be summarized descriptively by treatment group for each sampling time point using the PK analysis set.

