**13. Appendices**

### Appendix A. Analytical Window for Evaluation

Per protocol, visits are to be performed within 3 days of the protocol-specified study day. To allow for variations in scheduling, the following visit windows will be applied to selected efficacy and safety evaluations (ie, vital signs, laboratory evaluations) to assign a most appropriate nominal visit for analysis. If more than one assigned visit falls within the same defined window, the closest visit to the target day (ie, scheduled visit week  $\times$  7 + 1) will be considered for analysis. If two assessment dates are the same distance from the target day, then the latest visit will be considered for analysis. If more than one evaluation falls on the same date and time for laboratory results, then the value with the smallest accession number will be used.

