#### Analysis window for Vitals

Visit Week	Target Day	Window Definition
Baseline	1	Last Evaluation prior to or on Study Day 1
Week 2	15	Study Day 2 to 21
Week 4	29	Study Day 22 to 35
Week 6	43	Study Day 36 to 49
Week 8	57	Study Day 50 to 63
Week 10	71	Study Day 64 to 77
Week 12	85	Study Day 78 to 91
Week 14	99	Study Day 92 to 105
Week 16	113	Study Day 106 to 119
Week 18	127	Study Day 120 to 133
Week 20	141	Study Day 134 to 147
Week 22	155	Study Day 148 to 161
Week 24	169	Study Day 162 to 175
Week 26	183	Study Day 176 to 189
Week 28	197	Study Day 190 to 203
Week 30	211	Study Day 204 to 217
Week 32	225	Study Day 218 to 231
Week 34	239	Study Day 232 to 245
Week 36	253	Study Day 246 to 259
Week 38	267	Study Day 260 to 273
Week 40	281	Study Day 274 to 287
Week 42	295	Study Day 288 to 301
Week 44	309	Study Day 302 to 315

Week 46	323	Study Day 316 to 329
Week 48	337	Study Day 330 to 343
Week 50	351	Study Day 344 to 357
Week 52	365	Study Day 358 to 385
Week 58	407	Study Day 386 to 448
Week 70	491	Study Day 449 to 494

Analysis window for EASI and IGA

Visit Week	Target Day	Window Definition
Baseline	1	Last Evaluation after Randomization and prior to or on Study Day 1
Week 4	29	Study Day 2 to 35
Week 6	43	Study Day 36 to 49
Week 8	57	Study Day 50 to 63
Week 10	71	Study Day 64 to 77
Week 12	85	Study Day 78 to 98
Week 16	113	Study Day 99 to 140
Week 24	169	Study Day 141 to 210
Week 36	253	Study Day 211 to 294
Week 48	337	Study Day 295 to 343
Week 50	351	Study Day 344 to 357
Week 52	365	Study Day 358 to 427
Week 70	491	Study Day 428 to 494

Analysis Window for SCORAD, EQ-5D-3L, POEM, DLQI and PGI-S

Visit Week	Target Day	Window Definition
Baseline	1	Last Evaluation prior to or on Study Day 1
Week 4	29	Study Day 2 to 42
Week 8	57	Study Day 43 to 70
Week 12	85	Study Day 71 to 98
Week 16	113	Study Day 99 to 140
Week 24	169	Study Day 141 to 210
Week 36	253	Study Day 211 to 294
Week 48	337	Study Day 295 to 343
Week 50	351	Study Day 344 to 357
Week 52	365	Study Day 358 to 368

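### In Part A the TCS/TCI rule starts at day 29 at every time point, so prohibited use that ended by day 28 neither voids a week 4-12 response nor censors time to EASI 50/75/90

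*SAP*

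**What the plan says.** SAP 5.5 derives the week-16 primary endpoints as responses without TCS/TCI rescue from day 29 to week 16. SAP 5.6 carries that derivation to earlier visits, "when the time point of interest is week 4, week 6, week 8, week 10, and week 12 instead of week 16", and states that "the use of TCS/TCI will be considered from day 29, to those time points respectively". SAP 5.4 discards IGA and EASI scores on and after TCS/TCI rescue only when that rescue is from day 29. For the secondary endpoint of time to EASI 50/75/90, SAP 9.5.2 states: "Subjects who receive rescue medication from day 29 will be censored at the point when subjects receive rescue medication".

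The protocol is stricter about the earlier period. Under Protocol 3.1, Part A "subjects will wash out from TCS and are required to abstain from TCS use for 16 weeks". Protocol 7.1.7 prohibits TCS and TCI in Part A, and Protocol 7.1.5 adds: "Rescue is not allowed in the first 4 weeks of Part A".

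On timing, the Schedule of Activities says: "The window for visits is ± 3 days". SAP Appendix A gives the week-4 EASI/IGA assessment a target of day 29 and an analysis window of "Study Day 2 to 35".

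**The concern.** The start date suits week 16 but does very little at week 4, where the interval opens on the target day of the visit it is meant to protect. Suppose a Part A subject applies a topical steroid on days 15 to 28, against the protocol, and shows a 60% EASI reduction on day 29. Under the stated rules the score is kept, no TCS use is found, and an EASI 50 event is recorded at day 29. Time to EASI uses first attainment, so nothing later removes that event. Rescue begun on or after day 29, which the protocol allows, would void later scores and censor the subject. Use that the protocol forbids is thus handled more leniently than use that it permits.

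At stake is whether the early part of the response curve describes monotherapy. Protocol 3.1 gives reduced confounding by TCS as a reason for the Part A design.

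**Working it through.** **Inputs.** Target day = week × 7 + 1 (SAP Appendix A). Visit window ±3 days (Schedule of Activities). Week-4 EASI/IGA analysis window, days 2 to 35 (SAP Appendix A). Rule start, day 29 (SAP 5.4, 5.6, 9.5.2). About 60 subjects per arm (SAP 3.2).

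**Step 1: reproduce the plan's figure.** 4 × 7 + 1 = 29, as tabled. The formula also returns the tabled targets for weeks 6, 8, 10, 12 and 16.

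**Step 2: days covered.** For an assessment on day d, days covered = max(0, d − 29 + 1).

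| Visit | Target day | Days covered at target | Days 1-28 as share of days to target |
|---|---|---|---|
| Week 4 | 29 | 1 | 28/29 = 97% |
| Week 6 | 43 | 15 | 28/43 = 65% |
| Week 8 | 57 | 29 | 28/57 = 49% |
| Week 10 | 71 | 43 | 28/71 = 39% |
| Week 12 | 85 | 57 | 28/85 = 33% |
| Week 16 | 113 | 85 | 28/113 = 25% |

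**Step 3: week 4 off target.** Visits within ±3 days fall on days 26 to 32. Coverage is 0 days on days 26, 27 and 28, and 1, 2, 3 and 4 days on days 29 to 32. Of the 34 days in the analysis window (2 to 35), 27 have no look-back. The longest look-back is 35 − 29 + 1 = 7 days.

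**Step 4: what escapes.** At weeks 6 to 12, use that continues on or after day 29 is caught, so only use that ended by day 28 escapes. At a week-4 assessment before day 29 the interval has not opened, so any use escapes at that visit.

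**Step 5: is there another safeguard?** Table 2-1 places the first post-baseline EASI at week 4, so the earliest scheduled time-to-EASI event falls at the least protected visit. The FAS for Part A keeps all randomized subjects (SAP 6.1). Important deviations are tabulated by group (SAP 8.4), with no stated effect on response. TCS/TCI exposure is summarised by group (SAP 9.6.8, 9.6.9), but not for days 1 to 28 in particular. The only supporting set named for the primary endpoints, the mFAS, is described in SAP 9.5.1.1 as a possible COVID-19 analysis. SAP 6.3 to 6.6 were not in the text available for this check, so the mFAS definition could not be read.

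**Step 6: size, by assumption only.** The documents give no rate of use on days 1 to 28. Responders reclassified per arm = 60 × P(use only on days 1-28) × P(response given use).

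- Low: 60 × 0.02 × 0.10 = 0.12 subjects (0.2 points).
- Middle: 60 × 0.05 × 0.30 = 0.9 subjects (1.5 points).
- High: 60 × 0.20 × 0.50 = 6 subjects (10 points).

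This counts subjects who would be reclassified. As a measure of steroid-induced response it is an upper bound, because some would have responded anyway.

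**The case against.** Day 29 is a deliberate choice. SAP 2.1 dates the rescue intercurrent event from day 29 and describes the secondary estimands in the same way. Because rescue is not allowed in the first 4 weeks, day 29 is the first day on which permitted rescue can occur. Earlier use is a deviation, and analysing all randomized subjects despite deviations is an ordinary choice. This stands: the date is not a drafting slip. It does not explain why an interval framed for week 16 should also govern week 4, where it covers one day at target.

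The stakes are also limited. Weeks 4 to 12 IGA 0/1 and EASI 75 are not listed endpoints. Time to EASI is summarised by Kaplan-Meier curves, and SAP 9.5 makes any testing of secondary endpoints nominal and descriptive. This stands too, and it limits the weight of the point.

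A day-1 rule has its own cost. A subject with one application on day 3 would be censored before any scheduled EASI and lose credit at weeks 4 to 12, yet could still be a week-16 responder. Censoring at use may be informative. This is why both versions should be reported.

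**Conclusion.** The gap is real. In Part A, nothing in the available text voids a week 4-12 IGA 0/1 or EASI 75 response, or censors time to EASI 50/75/90, for prohibited TCS/TCI use that ended by day 28. At the week-4 target the rule covers 1 of 29 days. These day counts follow from the documents; the effect on response rates cannot be computed from them.

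A reader might infer more, in three ways that the documents do not support:

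- **That the rule is empty at week 4.** It is empty only for assessments before day 29, and reaches up to 7 days at the window edge.
- **That the early contrast is biased toward no effect.** That would need more early use on placebo. Protocol 3.1 reports greater TCS use on placebo in the earlier phase 2a study, but TCS was permitted there. It says nothing about how often, or in which arm, prohibited use would occur here.
- **That the week-16 primary result is compromised.** The primary derivation shares the day-29 start (28 of 113 days uncovered), but the use in question ended about 12 weeks before that assessment, so little effect is expected.

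This is an inexpensive improvement to a descriptive secondary analysis and to unlisted early-visit summaries.

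**What to change.** For Part A only, in time to EASI 50/75/90 (SAP 9.5.2) and in IGA 0/1 and EASI 75 at weeks 4 to 12 (SAP 5.6), count any recorded TCS/TCI use from Study Day 1 and handle it as use from day 29 is handled now. Show the current day-29 version alongside. Limit the matching change in SAP 5.4 to these analyses, because the same IGA and EASI scores feed the week-16 derivation. Leave the week-16 primary derivation as it is, and add a day-1 look-back version as a sensitivity analysis. Part B is outside the change, since TCS is allowed there after day 1 activities.

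The cost is SAP wording, one date condition in programming and the paired outputs. Protocol 7.8.2 already collects concomitant therapy from the first dose, so no new data are needed and nothing changes for subjects. The SAP should state that early-visit and week-16 status can disagree for a subject with brief early use, and that censoring at use may be informative.
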